4.0 MATERIALS AND METHODS

After a patient consents, the patient will be registered and entered into the project database and assigned an identification number. The subject's identification number will be used on all subject-specific documents and research-related forms.

During registration, patients will be randomized to two arms (Arm A: Usual Care Arm B: Health Care Coach Intervention). Specifically, the patients will be randomized into two arms by cancer type.

All patients will be surveyed over the course of the study regarding patient experience with care, patient satisfaction and overall health status and emotional and mental health status (using the CG-CAHPS: Clinician and Group Consumer Assessment of Healthcare Providers and Systems), advanced care planning, and symptom assessments (using the ESAS: Edmonton Symptom Assessment Scale) and healthcare use. A member of the project team, excluding the Health Care Coach, will administer the assessments and conduct an electronic health record review of all health care use at baseline, 3, 6, 9 and 12 months post-enrollment. Participants will provide consent for health record review at external facilities by signing a health release authorization form at each of the outcome assessment time periods. The symptom assessments will be administered at baseline for each patient in the intervention and control. Participant information should be entered into the local databases within 7 calendar days.

Arm A: Usual Care (Control) / No Intervention
 Patients in this arm receive "usual" care from their care team.

Arm B: Health Care Coach Arm / Intervention Group

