The intervention will be comprised of a health care coach assignment with a baseline introduction (either telephonic or in-person) of the program followed by a visit (telephonic or in-person) with the health care coach within 1 week after the first oncology appointment or after a patient has recurrent disease to discuss goals of care. The health care coach is trained in engaging patients and families in goals discussion and in symptom management algorithms. The health care coach will use standardized educational information to inform contacts with the patient including PREPARE for your care and other educational content as determined by the study team. The health care coach will contact patient based on patients' ongoing needs (i.e. weekly to monthly) and will conduct symptom assessments based on patients' treatment plans and symptoms for 6-months post-enrollment. All symptoms that are scored 4 or above and/or change by 2 points from a prior assessment will be reviewed with the supervising nurse who will conduct standard usual care processes as determined by the facility. Health care coach will also conduct meetings with patient's family and caregivers at the same time intervals as needed and upon request. All health care coach interactions will be logged and will include date of the interaction, details of the interaction, and the duration of the interaction.

Choosing the Health Coach:

Possible health coaches are identified by [name], the site PI. Candidate health coaches are educated fully about the project and the workflow. Health coaches who are interested in engaging in this study are appointed. Health coaches do not need to have a clinical background to engage in this study.

Training the Health Coach:

The oncology care team of a triage RN, APN/PA, or PI will train the health care coaches and provide standardized training manuals. The manuals include a highly detailed workflow of the project, from enrollment to completion. Coaches will learn about what to say during patient contact, advanced care planning conversations, the administration of various psychosocial questionnaires, the study calendar, data management, and key contact information.

Supervising the Health Coach:

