The health care coach will be supervised by the triage RN or APN/PA who provides oncology treatment support and also training. The triage RN or APN/PA will ensure that the protocol is carried out correctly and address any issues that may arise in the health care coach's workflow. The health care coach will participate in weekly meetings with the health coach in addition to daily supervision and will participate in monthly meetings with the rest of the project members (at both Stanford and St. Jude) to review study accrual and program goals. At these meetings, the health care coach will be responsible for providing a report on project progress and project issues.

Psychometric Measures

- 1. The Consumer Clinician and Group Consumer Assessment of Healthcare Providers and Systems (CG-CAHPS) will be used to assess patient satisfaction, overall health status, and overall emotional and mental health status. Information about the measure can be found here: https://cahps.ahrq.gov/Surveys-Guidance/CG/index.html
- 2. The Edmonton Symptom Assessment Scale (ESAS) will be used to measure the presence and degree of pain symptoms. The ESAS will be administered to the control group (at 0 months of diagnosis) and intervention group (every 2 weeks). The health care coach will embed the ESAS results for the control and intervention groups into Allscripts and alert the patient's provider that the results are available and if an issue exists.

[name] has used both of these measures with success before with a similar project completed at the Palo Alto Veterans Hospital (Palo Alto, CA). Information about this measure can be found here: http://www.npcrc.org/files/news/edmonton_symptom_assessment_scale.pdf

If patients feel discomfort while conducting their surveys they may choose to not complete them. If there are any psychological events that occur during the study, these will be reported to the NPOD and MOD via the site PI.

Site PI: [name]

[name] is responsible for site study supervision as well as the following: conducting biweekly meetings with all study members, troubleshooting recruitment and follow-up challenges, training the health care coaches, ensuring proper data collection, and general upkeep. The site PI is also responsible for interacting with the protocol director at Stanford, [name]. As this is [name] conception, and she piloted at another site, she will be able to provide [name] with specific advice and recommendations should challenges arise.

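### If the arm-specific ESAS schedule is followed, controls have no score after baseline and symptom change cannot be compared between arms

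*Combined protocol and SAP*

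**What the plan says.** Section 4.0 describes ESAS timing in three places.

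- **General survey text.** "All patients will be surveyed over the course of the study regarding patient experience with care", and the list that follows includes "and symptom assessments (using the ESAS: Edmonton Symptom Assessment Scale) and healthcare use". The next sentence states that "A member of the project team, excluding the Health Care Coach, will administer the assessments" and gives the times: "will administer the assessments and conduct an electronic health record review of all health care use at baseline, 3, 6, 9 and 12 months".
- **Baseline sentence, same paragraph.** "The symptom assessments will be administered at baseline for each patient in the intervention and control". It names no later time for either arm.
- **Psychometric Measures.** "The ESAS will be administered to the control group (at 0 months of diagnosis) and intervention group (every 2 weeks"). This is the only sentence that sets a separate schedule for each arm.

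Two further statements concern how the scores are used. In Arm B, "All symptoms that are scored 4 or above and/or change by 2 points from a prior assessment will be reviewed with the supervising nurse". For both arms, "The health care coach will embed the ESAS results for the control and intervention groups into Allscripts", with an alert to the patient's provider.

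Section 5.1, under the primary outcome measure, lists change in symptom assessments over the study among the items to be compared, next to hospitalizations, emergency department visits and several coach-contact measures. Section 5.2 does not name the ESAS. Its analysis of patient-reported change runs from baseline to 6 months.

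**The concern.** A change score needs at least two measurements. If staff follow Psychometric Measures, a control patient has one ESAS score and Arm B has a series. What remains is an uncontrolled trend in Arm B, which cannot separate the coach's effect from response to cancer treatment, the course of the disease, or the loss of the sickest patients through death. No later analysis can recover scores that were never collected.

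Symptom change is of interest even though it is not a stated aim: Section 2.0 names better and more timely symptom control as a desired result of the program, and symptom assessment is part of what the coach delivers.

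A second issue is that the Arm B scores trigger nurse review. They are therefore part of the intervention and not a neutral outcome measurement. Even if controls had later scores, coach-collected Arm B scores would be a poor comparator for scores collected by someone else for another purpose.

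**Working it through.** The plan gives no figure for the ESAS: no standard deviation, target difference or retention rate. There is nothing to reproduce. The check compares the schedules and then asks what the fix would deliver.

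**1. Control scores under each reading of Section 4.0**

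| Reading | Control ESAS times | Post-baseline scores per control | Controls with a possible change score |
|---|---|---|---|
| Psychometric Measures governs | 0 months | 1 − 1 = 0 | 64 × 0 = 0 |
| Baseline sentence read as the whole schedule | baseline | 0 | 0 |
| General survey text governs | baseline, 3, 6, 9, 12 months | up to 4 | up to 64 |

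The 64 per arm comes from Sample Size Considerations in Section 5.2. Under the first two readings the between-arm difference in change cannot be estimated at any sample size. Under the third the control data exist, and the Psychometric Measures sentence is simply wrong. The protocol does not say which reading applies.

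**2. What one 6-month ESAS in both arms would give**

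Inputs: two-sided alpha 0.05; outcome in SD units; a two-sample t comparison of 6-month scores, first without baseline adjustment. Retention is an assumption, shown as a range.

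- 95% CI half-width = t(0.975, 2n − 2) × √(2/n). At n = 64: 1.979 × √(2/64) = 0.350 SD.
- The difference detectable with 80% power is from the noncentral t distribution.

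| Assumed retention | n per arm | CI half-width (SD) | Detectable at 80% power (SD) |
|---|---|---|---|
| 100% | 64 | 0.350 | 0.499 |
| 70% | 0.70 × 64 = 44.8, taken as 45 | 0.419 | 0.597 |
| 50% | 32 | 0.500 | 0.711 |

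Adjusting for baseline multiplies these by about √(1 − r²), where r is the baseline-to-6-month correlation (also an assumption). At full retention the detectable difference becomes 0.499 × 0.954 = 0.48 SD for r = 0.3, 0.499 × 0.866 = 0.43 SD for r = 0.5, and 0.499 × 0.714 = 0.36 SD for r = 0.7.

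These figures describe the precision of the remedy. They do not measure harm in the current plan.

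**3. Added data collection, relative to Psychometric Measures**

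Baseline is already given to both arms. One 6-month form: 128 × 1 = 128 at most. All four later visits: 128 × 4 = 512 at most.

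**The case against.** The strongest reply is that no planned between-arm ESAS analysis exists to be lost. The ESAS appears in neither the aims and hypothesis (Section 1.0), nor the named secondary outcomes (Section 5.1), nor the analysis plan (Section 5.2). The only hook is one loosely worded list in Section 5.1. That list also holds time to first coach contact and the duration and frequency of contacts, which can exist only in Arm B, so its word for comparison cannot mean between arms for every item. A process measure is a natural reading. This stands, and it is why relabelling is an acceptable remedy.

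Second, the baseline-only schedule for controls may be deliberate. The separate baseline sentence would be redundant if the 3-monthly schedule already covered the ESAS, so it may be an exception that agrees with Psychometric Measures. Repeated ESAS with nurse review is part of the intervention, and withholding it from controls limits contamination. This also stands as a plausible intent. It does not remove the conflict with the general survey text, or with Section 5.1 if a between-arm comparison was meant.

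Third, Section 5.2 refers to an attached detailed SAP, and Section 4.0 mentions a study calendar in the coach training. Neither is in the combined document, and either might settle the schedule. The protocol's own sentences would still need to agree.

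A reader might infer that the trial's primary comparison is compromised, because symptom change is listed under the primary outcome measure. The documents do not support that: Section 5.2 builds the primary analysis on emergency department visits and hospitalizations within 6 months, with no ESAS input. A reader might also infer that a single 6-month ESAS fully repairs the item. It does not, because Section 5.1 refers to change over the whole study, follow-up runs to 12 months, and the 6-month scores come only from patients alive and responding. Deaths before then can bias the contrast as well as widen it.

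**Conclusion.** The concern holds in conditional form and is minor. If the Psychometric Measures schedule is followed, no control has a post-baseline ESAS, and the symptom change listed in Section 5.1 cannot be compared between arms. If the general survey text governs, the data exist and only the Psychometric Measures sentence needs correcting. Either way the text should be reconciled, because sites could follow either schedule and uncollected scores cannot be recovered.

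With one 6-month score in both arms, an unadjusted comparison has a 95% CI half-width of 0.35 SD at full retention and 0.50 SD at an assumed 50%. That is reasonable for an exploratory estimate but not for a confirmatory claim. Confidence is medium, because a within-Arm-B process measure may have been what the authors meant.

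**What to change.** Amend Psychometric Measures so that the non-coach assessor gives the ESAS to both arms at baseline and at least at 6 months, ideally at every visit already scheduled in Section 4.0. Then state the following:

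- Only these scores enter the between-arm comparison, which is exploratory and adjusted for baseline.
- Coach-collected Arm B scores are intervention-delivery data.
- With a single 6-month score, the contrast is baseline to 6 months among patients alive and responding, and does not describe change throughout the study.
- Follow-up control scores are not routinely uploaded with a provider alert, except through a usual-care safety route for severe scores.

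The cost is one short form per patient per added visit (at most 128 for the 6-month visit), slight extra burden on ill patients, and a small contamination risk from the safety route. No new visit or staff role is needed.

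If the sponsor does not want a between-arm symptom comparison, keep the Psychometric Measures schedule, label symptom change in Section 5.1 as a within-Arm-B process measure, and align the general survey text in Section 4.0. That is a text edit; its only cost is giving up the comparison.

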5.0 STATISTICAL CONSIDERATIONS

Biostatistician: [name] PhD and [name] (Stanford University)

5.1 Outcome Measurements

None of the listed outcomes relate to safety:

Primary Outcome Measure

The specific key measurement used to measure the effect of the intervention corresponding to the primary outcome is acute care utilization. Utilization will be measured evaluating comparisons of hospitalizations, emergency department visits, referrals to hospice and palliative care, time to first contact with care coach, duration of care coach contacts, frequency of care coach contacts, and symptom assessment changes throughout the study and time to intervention. Electronic health record review at the facility, review of health records at external facilities, and patient-report will be utilized to assess dates and utilization of all acute care use, hospice and palliative care use at each of the specified assessment time periods.

Secondary Outcome Measures

The specific key measurements corresponding to the secondary objective are several patient-reported outcome tools:

Satisfaction with Care and decision making and overall health and emotional and mental health status: CAPHS-G will be used to assess satisfaction with care, overall health status, and overall emotional and mental health status among patients at each of the specified time periods after enrollment. A 6 question satisfaction with decision making scale will also be administered at these time points.

Qualitative data regarding implementation will be assessed through 2 focus groups during the study. This may include patients, caregivers, providers, and staff at the site of implementation. Pl and study team from Stanford will provide oversight on analysis and data collection.

5.2 Analysis Plan (see Detailed Statistical Analysis Plan Attached)

All patients will be included in the analysis based on their randomization assignment at time of enrollment. The unit analysis will be completed at the participant-level. We will conduct descriptive statistics to evaluate balance between demographic (i.e., sex, age, race/ethnicity) and clinical variables (i.e., stage of cancer, diagnosis of cancer) between both the randomized and control groups. To assess our primary outcome of the effect of the intervention on acute care use within 6-months post-enrollment we will assess % of patients with acute care use. We will create a (composite measure for acute care use that includes both ED visits and hospitalizations. To compare risk of acute care use (composite measure) and individual ED and hospital use within 6 months post-enrollment, we will use Cox regression models. We will also compare counts of total ED visits and hospitalization (composite measure of acute care use) within the first 6 months, using General Estimating Equation with Poisson family, log link, and independent correlation.

For secondary outcomes of ED and hospital use within 12 months, we will compare use using GEE models. We will compare counts of total ED visits and hospitalization (composite measure of acute care use) within 12 months, using General Estimating Equation (Poisson) with an offset term for length of follow-up. To compare goals of care discussion and documentation, Advance Directive

documentation, Physician Order for Life Sustaining Treatment documentation, Chemotherapy, Radiation, Surgery, hospice, and palliative care within 12 months, we will use GEE models to compare odds of documentation or use across groups. For end-of-life health care use, we, we will compare any ED use and hospital use prior to death (30 days prior) and proportion of participants with palliative care and hospice use using the models described above among participants who died during the 12-month study.

For secondary outcomes, we will assess change in patient-reported outcome scores from baseline (at time of enrollment) to 6-months (post-enrollment). For satisfaction variables with responses "never", "sometimes," "usually," or "always" we will report results as the proportion of participants who respond "always" at 6-months post-enrollment compared to all other responses. For satisfaction variables with responses, "strongly disagree," "disagree," "neither agree nor disagree," "agree," or "strongly agree, we will report results as the proportion of participants who respond, "strongly agree." For overall health and overall mental and emotional health variables, responses are scores that range from 0 to 5, with lower scores indicating "very good" or "excellent" health and higher scores indicate poorer overall health. We will report results as the proportion of participants who respond, "very good" or "excellent." Missing data will not be imputed in any case. We will utilize GEE to compare changes between groups overtime from baseline (time of enrollment) to 6-months post-enrollment using GEE models with a term for an interaction between the treatment group and time (month) and clustered within person.

We will compare survival using Kaplan Meier methods and the risk of death for both groups after randomization using Cox proportional hazards regression models. All analyses will be adjusted for covariates that are found to be imbalanced between study groups, such as age, race/ethnicity, cancer stage and cancer diagnosis.

Relevant subsets of the above metrics may be measured on patients by cancer diagnosis and stage.

Sample Size Considerations

The sample size of 128 participants (64 randomized to the intervention group and 64 randomized to the control group) provides greater than 90% power to detect a 55% or greater difference in acute care use risk at 6-months follow-up. The anticipated effect size was based on our prior studies [11, 13, 18] and feedback by the oncology clinicians at St. Jude's Crosson Cancer Institute. Power calculations will not be generated for our secondary outcomes as these are considered exploratory. Statistical significance of secondary outcomes is for trends only and not represented in this sample size calculation.

Interim analyses every 6 months will evaluate point estimates and trends to inform refinements to the protocol. Descriptive statistics and exploratory data analyses will be conducted as needed to evaluate protocol process measures with key outcomes identified.

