1.0 SPECIFIC STUDY AIMS

Aims

The primary aim is to reduce acute care utilization and cost for advanced cancer patients by training and deploying health care coaches who help patients and families discuss care goals, virtual modalities, engage in shared-decision-making, and participate in educational activities.

The secondary aims are to improve patients' experience of their care including overall health and emotional and mental health status, improve patient satisfaction with care and decision-making and advance care planning.

Hypothesis

Compared to patients who receive usual advanced cancer care, patients who partner with lay health care coaches are hypothesized to experience lower rates of acute care utilization, lower numbers of emergency room visits and hospital stays within 6-months post-enrollment. Secondarily, we will explore the effect of the intervention on satisfaction with care, overall health and emotional and mental health status, from time to enrollment to 6 months post-enrollment, advance care planning documentation, and acute care use at 12-months post-enrollment and within 30 days prior to death among those who died during the 12-month follow-up period.

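### The end-of-life comparison is made only among patients who died, so randomization does not protect it; its 30-day look-back also has no lower limit at randomization.

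*Combined protocol and SAP*

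**What the plan says.** The Hypothesis in section 1.0 introduces the secondary outcomes with "Secondarily, we will explore the effect of the intervention on satisfaction with care". The list that follows ends with acute care use "within 30 days prior to death among those who died during the 12-month follow-up period".

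Section 5.2 gives the analysis: "we will compare any ED use and hospital use prior to death (30 days prior". It adds the proportions with palliative care and hospice use, "using the models described above among participants who died during the 12-month study".

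Four other statements bear on this:
- Section 5.2 opens with the general rule "All patients will be included in the analysis based on their randomization assignment at time of enrollment".
- It later plans a Kaplan-Meier and Cox comparison of death between the arms, and adjustment for covariates found imbalanced between the study groups.
- On the standing of these outcomes it says "Power calculations will not be generated for our secondary outcomes as these are considered exploratory".
- Section 4.0 has staff "conduct an electronic health record review of all health care use at baseline, 3, 6, 9 and 12 months post-enrollment", without saying how far back the baseline review reaches.

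Nothing in the text says where the 30-day window begins for a patient who dies soon after enrollment. Nor does it give this outcome a denominator of all randomized patients.

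**The concern.** Randomization makes the two arms comparable at enrollment. It does not make the patients who later die in one arm comparable with those who later die in the other. If coaching alters who dies within a year, the two groups of decedents differ in composition, and a difference in their last-month care may reflect that difference alone. Adjusting for covariates imbalanced between the study groups does not restore the protection. The survival comparison shows that the plan itself treats death as something that may differ by arm, yet section 1.0 presents the end-of-life contrast as part of exploring the effect of the intervention.

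The second issue is the window. Patients consent at an oncology visit after an advanced cancer diagnosis (section 3.1), and section 3.2 sets no life-expectancy criterion. For a death on day 10, a 30-day look-back contains 20 days before randomization. An emergency visit or admission in those days could be counted as end-of-life use in the assigned arm, although the coach could not have influenced it.

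At stake is the interpretation of one named secondary outcome.

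**Working it through.** The documents state no figure for this outcome and no death rate, so there is nothing of the plan's own to reproduce. The power statement in 5.2 and 5.3 concerns acute care use at 6 months and does not depend on this analysis.

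**1. Selection by death.** The inputs are hypothetical and chosen so that coaching changes no patient's end-of-life use. Suppose 30% of patients would die within 12 months in either arm, with acute care use of 50% in the last month. A further 10% would die only under usual care.

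- If the further 10% have use of 80%: usual-care decedents (0.30 × 0.50 + 0.10 × 0.80) / 0.40 = 0.575; coached decedents 0.50; ratio 0.50 / 0.575 = 0.87.
- If the further 10% have use of 30%: usual-care decedents (0.15 + 0.03) / 0.40 = 0.45; ratio 0.50 / 0.45 = 1.11.
- If coaching does not change who dies: ratio 1.00.

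The true ratio is 1.00 throughout. The false departure can go either way, depending on who the extra decedents are.

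With all randomized patients as the denominator, the first case reads as follows:

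| | Alive at 12 months | Died with acute care in last 30 days | Died without it |
|---|---|---|---|
| Usual care | 60% | 0.15 + 0.08 = 23% | 0.15 + 0.02 = 17% |
| Coach | 70% | 15% | 15% |

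Here the reader can see that the arms differ in deaths, which the decedent-only ratio hides.

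**2. Windows that cross randomization.** Inputs: 128 patients, 64 per arm (5.2); 30-day window (5.2). 12-month mortality *m* and a constant hazard are assumptions.

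- Hazard per year: h = −ln(1 − m).
- Share of decedents who die within 30 days of enrollment: [1 − exp(−h × 30/365)] / m.
- Early deaths in the trial: 128 × m × that share.
- Share of all look-back time before randomization: the mean over decedents of (1 − t/30) for deaths on day t < 30, and 0 otherwise.

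| m | Deaths in 128 | Share within 30 days | Early deaths in 128 | Look-back time before randomization |
|---|---|---|---|---|
| 20% | 25.6 | 9.1% | 2.3 | 4.6% |
| 30% | 38.4 | 9.6% | 3.7 | 4.8% |
| 40% | 51.2 | 10.3% | 5.3 | 5.2% |
| 60% | 76.8 | 12.1% | 9.3 | 6.1% |

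At m = 30% there are 64 × 0.30 = 19.2 decedents per arm, of whom about 1.85 are early deaths. One misclassified patient moves an arm's percentage by 1 / 19.2, about 5 points. A shift of about 10 points needs two, which is roughly every early death in that arm. Because the outcome is any use, an early decedent is misclassified only with acute care in the window before randomization and none between randomization and death. The documents give neither probability.

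**The case against.** The strongest reply is that the plan asks little of this comparison. Secondary outcomes are exploratory and unpowered, and their significance is for trends only. Survival is compared by arm, so a reader can judge whether the decedent groups may differ. Comparisons of emergency, hospital, hospice and palliative care use over 12 months, not limited to decedents, are already planned. All of that stands, and it limits how much weight the point carries. But an exploratory label removes the need for power. It does not turn a contrast conditioned on a post-randomization event into an estimate of effect.

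On the window, a reader might infer that the plan does credit care before randomization to an arm. The documents do not support that. The text is silent, section 1.0 ties the outcome to the follow-up period, and the reach of the baseline record review is not given. The detailed analysis plan that the 5.2 heading calls attached is not in the text reviewed and may contain a rule. The wording permits such counting and does not require it. Unless early deaths differ by arm, the resulting error is expected equally in both arms and would mostly be noise or dilution.

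A reader might also infer that the models referred back to cannot handle a window counted back from death. That does not hold either. Section 5.2 names GEE models for odds of use just before this passage, and these can handle a yes/no outcome, although the plan could say more exactly which model it means.

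**Conclusion.** The concern holds. The main point is the restriction to patients who died: the comparison is not protected by randomization and should not be reported as an effect of coaching. Its possible size cannot be taken from the documents. The ratios 0.87 and 1.11 are illustrations that rest on coaching changing who dies. A reader might infer that the comparison is certainly biased, but nothing in the documents shows that coaching affects mortality, and without such an effect the ratio in the illustration is 1.00.

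The open window is secondary. It touches about 9% to 12% of decedents, or 2 to 9 of 128 patients, under a constant hazard and 12-month mortality of 20% to 60%. Deaths concentrated early would raise that share, and deaths concentrated late would lower it. A 10-point shift in one arm is near the worst case and should not be taken as typical. The primary result, sample size and stated power are unaffected.

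**What to change.** In section 5.2:

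1. Start the window at the later of randomization and 30 days before death, and state how a hospital stay already under way at randomization is counted. Add a sensitivity analysis that excludes deaths within 30 days of randomization. No offset for days observed is needed, because the outcome is any use and not a count.
2. Label the decedent comparison descriptive, including its palliative care and hospice proportions, and show the number of deaths by arm beside it. Align the Hypothesis in section 1.0 with that label.
3. Add a table by arm of all randomized patients with known 12-month status, in three classes: alive at 12 months, died with acute care in the last 30 days, died without it. Report the number with unknown status.

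Starting the window at randomization does not cure the selection by death, so items 2 and 3 are needed as well. The cost is some wording and one extra table. Dates of acute care use are already collected (section 5.1), and the survival analysis requires dates of death. The downside is small cells (at 30% mortality, about 19 deaths per arm split between two classes) and a more modest label for the decedent comparison.
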